10.2 Scheduled visits

This study consists of 5 visits (Group 1 - WLC) or 4 visits (Group 2 – initial treatment) over 6 or 9 months respectively (see Figure 1) Study procedures to be performed at each visit are detailed in the Schedule of Assessments and Procedures in Appendix 1.

Visits should be conducted within the specified visit windows where possible.

Figure 1: Study timeline and procedures. Nasal swab collection (blue arrow), blood collection (red arrow).

Group 1 (WLC)

Visit 1 – Screening and randomisation

The following assessments and procedures will be performed and recorded at this visit:

- Obtain written informed consent
- Evaluate inclusion and exclusion criteria
- Obtain demographic history
- Obtain medical history
- Vital signs
- Explain daily respiratory symptom data collection and assist with collection for Day 0

Once all screening procedures have been completed and eligibility confirmed, the participant will be registered with the Sponsor. Further information on the registration process is provided in the Study Reference Manual.

Visit 2: Treatment initiation 3 months post randomisation (±5 days)

- Update demographic & medical history
- Vital signs

- Nasal swab
- Collection of blood samples
- Dispense study medication and explain administration
- Adverse event assessment

Visit 3: Treatment cessation 6 months post randomisation (± 5 days)

- Vital signs
- Nasal swab
- Collection of blood samples
- Clarify any missing data (daily respiratory symptoms) with participant, if not previously addressed by email/SMS
- Adverse event assessment
- Collect used investigational product packaging and unused investigational product

Visit 4: Follow up cessation 9 months post randomisation (± 5 days)

- Vital signs
- Nasal swab
- Collection of blood samples
- Clarify any missing data (daily respiratory symptoms) with participant, if not previously addressed by email/SMS
- Adverse event assessment

Unscheduled Visit: at time of ARI necessitating workforce removal

- Vital signs
- Nasal swab
- Collection of blood samples
- Clarify any missing data (daily respiratory symptoms) with participant, if not previously addressed by email/SMS
- Adverse event assessment

Group 2 (Initial Treatment)

Visit 1 – Screening, randomisation, and treatment initiation

The following assessments and procedures will be performed and recorded at this visit:

- Obtain written informed consent
- Evaluate inclusion and exclusion criteria
- Obtain demographic history
- Obtain medical history
- Vital signs
- Nasal swab
- Collection of blood samples
- Drug delivery
- Dispense study medication and explain administration
- Explain daily respiratory symptom data collection and assist with collection for Day 0

- Adverse event assessment

Once all screening procedures have been completed and eligibility confirmed, the participant will be registered with the Sponsor. Further information on the registration process is provided in the Study Reference Manual.

Visit 2: Treatment cessation 3 months post randomisation (± 5 days)

- Vital signs
- Nasal swab
- Collection of blood samples
- Clarify any missing data (daily respiratory symptoms) with participant, if not previously addressed by email/SMS
- Adverse event assessment
- Collect used investigational product packaging and unused investigational product

Visit 3: Follow up cessation 6 months post randomisation (± 5 days)

- Vital signs
- Nasal swab
- Collection of blood samples
- Clarify any missing data (daily respiratory symptoms) with participant, if not previously addressed by email/SMS
- Adverse event assessment

Unscheduled Visit: at time of ARI necessitating workforce removal

- Vital signs
- Nasal swab
- Collection of blood samples
- Clarify any missing data (daily respiratory symptoms) with participant, if not previously addressed by email/SMS
- Adverse event assessment

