Serious Adverse Event Reporting Children's Health and Environment Program, (CHEP)
Child Health Research Centre
[contact]

2. Investigator Signature Page

Reducing acute severe respiratory events in health care workers during the Covid-19 pandemic with OM85

I confirm that I have read **Protocol Version 2.0 dated 12th June 2020**. As the site investigator, I understand it, and I agree to adhere to the study conduct requirements and agree to conduct this protocol in accordance with International Conference on Harmonization Good Clinical Practice E6 (ICH-GCP), the Declaration of Helsinki, the United States (US) Food and Drug Administration (FDA), and local regulations and guidelines. I agree to report all information or data in accordance with the protocol and in particular I agree to report any serious adverse events. I will accept the monitors, auditors and regulatory inspector's oversight of the study. I will promptly submit the protocol to the applicable ethical review board.

Chief investigator signature

[name] [name]

Chief investigator printed name

Date

This page has been left blank intentionally

3. Synopsis of Protocol

Title	A phase 3, multi-centre study testing the reduction of acute severe respiratory events in health care workers during the Covid-19 pandemic with OM85
Clinical phase	Phase Three
Protocol number	BV-2020/19
Principal Investigators	[name] [name] [name] Assoc [name] [name] [name] [name] Assoc [name] [name] [name]
Statistical consultant	[name]
Study design	Parallel group, Wait-list design, with treatment delayed for 3 months Participants will be randomized on a 1:1 ratio with 500 participants per group in Australia and 500 per group in the UK. Group 1: Wait-list control. One capsule OM85 (7.0 mg) will be given daily for 3 months, commencing in Month 3, with 3 months follow-up off treatment. Group 2: Initial treatment. One capsule OM85 (7.0 mg) will be given daily for 3 months, commencing on day 0, with 3 months follow-up off treatment.
Accrual objective	2000 Health Care Workers (HCW):- 1000 from Brisbane Hospitals 1000 from UK Hospitals

Accrual period	4 weeks
Study duration	12 months
Countries	Australia, United Kingdom
Sites	Queensland Children’s Hospital, Brisbane (Site Investigator: [name]) Imperial College Hospital, London (Site Investigator: [name]) Prince Alexandra Hospital, Brisbane (Site Investigator: [name]) Princess Charles Hospital, Brisbane (Site Investigator: Assoc [name])

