8.1 Description

This study will be conducted as a multi-centre, parallel group, wait list design clinical trial testing the reduction of acute severe respiratory events requiring workforce removal in HCW with OM85. Health Care Workers who are eligible will receive daily OM85 for 3 months. Group 1 “Wait-list group” will be given daily OM85 for 3 months commencing in Month 3, with 3 months follow-up off treatment. Group 2 “Initial treatment group” will be given daily OM85 for 3 months commencing in on day 0, with 3 months follow-up off treatment

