8.2.2 Secondary efficacy endpoints

Secondary endpoints include:

- The time to ARI necessitating workforce removal
- The proportion of HCW contracting an ARI necessitating workforce removal at end of treatment and at the end of the follow-up period, overall and by department
- The total number of days with respiratory symptoms (upper or lower)
- The proportion of HCW with COV infection documented by PCR, seroconversion and/or COV ARI necessitating workforce removal.
- The time to LRI necessitating workforce removal
- The proportion of HCW contracting an LRI necessitating workforce removal at end of treatment and at the end of the follow-up period, overall and by department
- The proportion of HCW with COV infection documented by PCR, seroconversion and/or COV LRI necessitating workforce removal.

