13.2.2 Statistical analyses

The *interim analysis*, undertaken at month 1 on both the "intention-to-treat" and "per protocol" groups, will examine the primary outcome: if the treatment difference is statistically significant in favour of OM85 the DSMB will consider immediately switching WLC participants to OM85.

Between-group differences in the primary outcome at 3 months will be assessed using log-binomial regression. Secondary outcomes measured to follow-up cessation will be assessed using mixed-effects models with group and stage (treatment/follow-up) (main effects and interaction) as fixed effects and HCW as random effect. Time-to-ARI analyses will use the log-rank test. Analyses will be undertaken on both the "intention-to-treat" and "per protocol" groups.

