Appendix 1: Schedule of Assessments and Procedures
Group =1 (Wait List Control)

	Recruitment and Randomisation	Treatment initiation	Treatment Cessation	Follow-up Cessation	Unscheduled visit
Visit	1	2	3	4	5
Day	0	90	180	270	
Visit Window		±5 days	±5 days	±5 days	
Informed consent	x				
Eligibility criteria	x				
Randomisation	x				
Medical history	x	x			
Demographic history	x				
Vital signs	x	x	x	x	x
Nasal swab		x	x	x	x
Study bloods		x	x	x	x
Drug delivery		x			
Drug distribution		x			
Drug collection			x		
Daily symptom data explained & first day completed	x				
Diary Daily symptom data reviewed		x	x	x	x
Adverse events		x	x	x	x

Group 2 (Initial Treatment)

	Recruitment Randomisation and Treatment	Treatment Cessation	Follow-up Cessation	Unscheduled visit
Visit	1	2	3	4
Day	0	90	120	
Visit Window		±5 days	±5 days	
Informed consent	x			
Eligibility criteria	x			
Randomisation	x			
Medical history	x			
Demographic history	x			
Vital signs	x	x	x	x
Nasal swab	x	x	x	x
Study bloods	x	x	x	x
Drug delivery	x			
Drug distribution	x			
Drug collection		x		
Daily symptom data explained & first day completed	x			
Diary Daily symptom data reviewed		x	x	x
Adverse events		x	x	x

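### Appendix 1 puts the Group 2 follow-up cessation visit at Day 120; the rest of the protocol puts it at 6 months, so the cell should read Day 180

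*Combined protocol and SAP*

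**What the plan says.** Four places in the protocol bear on when Group 2 finishes follow-up.

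- **Synopsis, study design.** Group 2 takes OM85 for three months "commencing on day 0, with 3 months follow-up off treatment".
- **Section 8.1.** The same schedule: OM85 daily "for 3 months commencing in on day 0, with 3 months follow-up off treatment".
- **Section 10.2, Group 2 visit list.** Treatment ends at 3 months, and then comes "Visit 3: Follow up cessation 6 months post randomisation", with a window of ±5 days.
- **Appendix 1, Group 2 table.** The day row reads 0, 90, 120 for the three scheduled visits, so follow-up cessation falls on Day 120, again ±5 days.

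The Group 1 table in Appendix 1 uses Days 0, 90, 180 and 270 for the visits that 10.2 places at randomisation and at 3, 6 and 9 months.

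The opening sentence of 10.2 names Group 1 first and Group 2 second, then gives their durations as "over 6 or 9 months respectively". Read literally, that assigns 6 months to Group 1 and 9 months to Group 2, the reverse of the visit lists below it.

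**The concern.** The text and the schedule table give different dates for the same visit, and the gap is far larger than the visit window. Section 10 and section 10.2 both send sites to Appendix 1, which is the only place that gives the follow-up visits as study-day numbers. A site could therefore book from the table. Section 15.4 treats a visit outside its window as a protocol deviation, so whichever date a site follows, the visit falls outside the other stated window.

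If the table were followed, the off-treatment stage to the final visit would be shorter in Group 2 than in Group 1. These items would be exposed:

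- the secondary endpoint "The proportion of HCW contracting an ARI necessitating workforce removal at end of treatment and at the end of the follow-up period", and its LRI counterpart;
- total days with respiratory symptoms;
- the group-by-stage models in 13.2.2 ("Secondary outcomes measured to follow-up cessation will be assessed using mixed-effects models"), for which no adjustment for time observed is stated;
- detection of seroconversion, because the last swab and blood sample would be taken early;
- safety data, because AE collection runs to the final visit (section 12) and SAE reporting runs 30 days past the end of participation (section 12.3).

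**Working it through.** **Inputs**

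- Group 2: 3 months of treatment from Day 0, then 3 months off treatment (synopsis, 8.1); follow-up cessation at 6 months ±5 days (10.2).
- Appendix 1, Group 2: Days 0, 90, 120, window ±5 days.
- Appendix 1, Group 1: Days 90, 180, 270 for months 3, 6, 9.
- Section 13.2: 20% infection assumed in Group 1, with no period stated.

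**Step 1: can Day 120 be reproduced?** The Group 1 table gives 90/3 = 180/6 = 270/9 = 30 days per month. Group 2 follow-up cessation is then (3 + 3) × 30 = Day 180. With calendar months it is 6 × 30.4375 ≈ Day 183. Neither gives 120, which is month 4 on the appendix's own scale.

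**Step 2: can one visit satisfy both?** Table: 120 ± 5 = Days 115–125. Text: 180 ± 5 = Days 175–185. The gap is 175 − 125 = 50 days, so no.

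**Step 3: what changes if the table is followed?**

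| Quantity | Table (Day 120) | Text (Day 180) |
|---|---|---|
| Group 2 off-treatment days | 120 − 90 = 30 | 180 − 90 = 90 |
| Group 1 off-treatment days | 270 − 180 = 90 | 270 − 180 = 90 |
| Group 2 AE collection ends | about Day 120 | about Day 180 |
| Group 2 SAE reporting regardless of cause ends | 120 + 30 = Day 150 | 180 + 30 = Day 210 |

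**Step 4: illustration of the effect on raw proportions.** Because 13.2 gives no period for its 20%, I assume a constant hazard h = −ln(0.8)/T and vary T. Risk over d days is 1 − exp(−h·d). With no drug effect, and counting events in the off-treatment stage only:

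| Assumed T | Group 2, 30 days | Group 1, 90 days | Ratio |
|---|---|---|---|
| 90 days | 7.2% | 20.0% | 0.36 |
| 180 days | 3.7% | 10.6% | 0.35 |
| 365 days | 1.8% | 5.4% | 0.34 |

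If the endpoint is instead read as cumulative from the start of treatment, the comparison is 120 days with 180 days: 25.7% vs 36.0% (T = 90), 13.8% vs 20.0% (T = 180) and 7.1% vs 10.4% (T = 365). The ratio is then about 0.68 to 0.72.

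**Step 5: does the opening sentence of 10.2 help?** No. Read literally it gives Group 2 nine months, which supports neither 120 nor 180. It is a separate reversed-order slip.

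**The case against.** The strongest reply is that the intended value is easy to recover. Section 10.2 states 6 months outright, the synopsis and 8.1 give it by addition, and the Group 1 table fixes the conversion to days. Section 10.2 also refers to Appendix 1 for the procedures at each visit and states the timing itself, so nothing makes the table take precedence. On this view the point is editorial. That stands as a limit on the likely harm. It does not remove the conflict: the protocol gives sites two dates for one visit and does not say which governs.

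Some points of detail also stand.

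- Under 12.3, SAEs after the 30-day period remain reportable if the investigator suspects the study drug. Only SAEs not suspected to be related would be lost between Days 150 and 210.
- Symptoms are collected by daily SMS (10.1.7) and ARIs at unscheduled visits, and no stop date for the SMS is given. The 30 days of observation is certain for the final swab, blood sample and AE collection, but it is an inference for symptoms and ARIs.
- The 20% in 13.2 is COV infection, not ARI with workforce removal. A constant hazard is also a crude assumption in a pandemic, particularly as the two groups' off-treatment stages fall in different calendar periods. The risks in Step 4 show direction and rough scale only.

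**Conclusion.** The concern holds. Day 120 contradicts 10.2, the synopsis, 8.1 and the day convention of the same appendix; the consistent value is Day 180. The error is 60 days against a ±5-day window. The Group 2 row has three values for its three scheduled visits, so nothing suggests a displaced entry, and no text supports a 4-month visit or a 1-month follow-up.

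If sites followed the cell, Group 2 would have one third of the intended off-treatment time to its final visit. Raw follow-up-stage proportions could then differ by a ratio of about 0.34 to 0.36 with no drug effect, or 0.68 to 0.72 on the cumulative reading. This is a worst case, not an expected bias. It requires every Group 2 participant to be scheduled from the table, observation to stop at that visit, a constant hazard, and a comparison of unadjusted proportions.

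The primary endpoint (analysed at 3 months, before the wait-list group starts treatment), the month-1 interim analysis and the sample size are untouched. The log-rank analyses can handle unequal follow-up by censoring. The point should be fixed because it touches secondary endpoints and safety follow-up, but it does not threaten the main result.

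**What to change.** - In Appendix 1, Group 2 table, change the Visit 3 day from 120 to 180 and keep the ±5-day window.
- In the opening sentence of 10.2, reverse the durations so that 9 months goes with Group 1 and 6 months with Group 2.
- Check that Figure 1 and the Study Reference Manual show the same days.

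Section 13.2.2 needs no change for this error: with Day 180 the off-treatment stage is 90 days in both groups. The cost is one table cell and one phrase, with no added visits and no change to the analysis.

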10.3 Early withdrawal visit

Participants who discontinue from the study for reasons other than ARI necessitating workforce removal, will be asked to attend an Early Withdrawal Visit. Where practicable, the study procedures scheduled for the current visit should be completed, or in the case of early withdrawal between visits, the procedures scheduled for the next study visit should be completed if the participant is agreeable.

For safety follow-up, participants should be encouraged to provide a blood sample. All used and unused study medication (including packaging) should be collected or arrangements made for its return to the clinic at this visit. Where possible, stop dates for ongoing AEs should be obtained.

11. Study treatment

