9.3 Criteria and procedures for participant withdrawal

9.3.1 Withdrawal of participants from study

Participants will be withdrawn from the study if any of the following conditions are met:

- The participant withdraws their consent
- The participant fails to return to the clinic (i.e., they are lost to follow-up or death)
- The site investigator or his/her designee believes that continuation in the study is no longer in the participant's best interests (which may be as a result of the occurrence of adverse events (AE) or clinically relevant laboratory results)
- The participant is unable to comply with the protocol, including completing required study treatments, procedures, tests and/or examinations
- The Sponsor reserve the right to terminate the entire study or any participants involvement at any time

Participants who prematurely discontinue investigational product will be encouraged to continue with the study visit schedule and assessments. For further information regarding Early Withdraw Visits refer to Section 10.4.

Those participants that cease the investigational product before the end of the study, but continue to be assessed for all other aspects of the study, will be regarded as members of the intention to treat (ITT) sample. All remaining study medication (including used and unused medication and packaging) will be collected.

In all cases, the reason and date of withdrawal from the study, or investigational product, will be completed in the source documentation and the CRF. If the withdrawal is due to an adverse event or a clinically significant laboratory result, the participant will be followed until the AE is resolved or is clinically stabilised. The AE or laboratory result must be recorded in the CRF.

If a participant tests positive to a clinical test (not part of the study) they will follow the hospital isolation protocol. The study Covid testing is done by measuring antibodies, which are not suitable for acute surveillance as it detects past infection. Results (positive or negative) will be returned to participant for their own information

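### Section 10.3 exempts workers who leave because of an ARI with workforce removal from the Early Withdrawal Visit, so for them no contact is specified after the acute visit

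*Combined protocol and SAP*

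**What the plan says.** Section 10.3 sets who is asked to a closing visit: "Participants who discontinue from the study for reasons other than ARI necessitating workforce removal, will be asked to attend an Early Withdrawal Visit". At that visit the procedures of the current or next scheduled visit are done where practicable and medication is returned. Two further lines are specific to leavers: "For safety follow-up, participants should be encouraged to provide a blood sample" and "Where possible, stop dates for ongoing AEs should be obtained". No date or interval is given for the visit.

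Section 9.3.1 opens its list with "Participants will be withdrawn from the study if any of the following conditions are met" and gives five conditions: consent withdrawn, failure to return, the investigator's judgement of best interest (which may follow an AE), inability to comply, and a sponsor decision. An ARI with workforce removal is not among them. The same section says of people who stop the product: "Participants who prematurely discontinue investigational product will be encouraged to continue with the study visit schedule and assessments". If withdrawal is due to an AE, "the participant will be followed until the AE is resolved or is clinically stabilised".

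Section 10.2 gives both groups a visit headed "Unscheduled Visit: at time of ARI necessitating workforce removal", with vital signs, nasal swab, blood, clarification of symptom data and AE assessment. Appendix 1 lists the same visit. On the study's antibody tests, section 9.3.1 says they are tests "which are not suitable for acute surveillance as it detects past infection".

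Section 13.3.1 analyses the primary endpoint at 3 months. Section 13.2.2 takes secondary outcomes to the end of follow-up.

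**The concern.** Sections 9.3.1 and 10.3 do not agree on whether an endpoint ARI is a way out of the study. No section says that daily SMS and scheduled visits continue after the Unscheduled Visit, so a site could read 10.3 as permission to close the participant at the event.

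For a worker who does leave at that point, the last specified contact falls during the acute illness. Its outcome is not yet known, and by the protocol's own account an antibody test looks backwards. What may be missing afterwards is a post-acute sample for seroconversion (part of a secondary endpoint and a mechanistic endpoint in its own right), symptom days, and AE stop dates.

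This loss is triggered by the primary outcome. If OM85 lowers ARI risk, fewer people are exposed to it in Group 2 than in Group 1. The mixed models in section 13.3.2 have group and stage as fixed effects and a random effect for the worker. Section 13 gives no missing-data method, so nothing in the plan deals explicitly with loss linked to an ARI.

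**Working it through.** **1. The plan's own figures (section 13.2).** Inputs: 20% in Group 1; 13.5% in Group 2 with 500 per group; a 25% reduction, so 0.20 × 0.75 = 15%, with 1000 per group; α = 0.05, taken as two-sided because the plan does not say.

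Power = Φ[(Δ − 1.96 × SE_pooled) / SE_unpooled].

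- 500 per group: Δ = 0.065; SE_pooled = √(2 × 0.1675 × 0.8325 / 500) = 0.02362; SE_unpooled = √((0.16 + 0.116775) / 500) = 0.02353. Power = Φ(0.795) = 78.7%, against a stated 80%.
- 1000 per group: Δ = 0.05; SE_pooled = 0.01699; SE_unpooled = 0.01696. Power = Φ(0.985) = 83.8%, against a stated 80%.

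The first figure is reproduced closely and the second is rounded on the safe side. This point does not depend on either; they supply the event rates below.

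**2. Samples available for a worker with an endpoint ARI before Month 3 who then leaves (section 10.2, Appendix 1).**

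| | Day 0 blood and swab | Acute visit | After the acute visit |
|---|---|---|---|
| Group 1 | none listed at Visit 1 | yes | none specified |
| Group 2 | yes | yes | none specified |

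A change in serology cannot be shown from one sample. In Group 1 there is neither a sample before nor a sample after. In Group 2 there is a sample before, but the second is taken at the acute illness. Ascertainment of seroconversion among these leavers is therefore weak in both arms and weaker in Group 1.

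**3. AE rules that still apply.** Section 10.1.7 records respiratory symptoms as AEs. Section 9.3.1 follows an AE that caused withdrawal to resolution or stabilisation. Section 12.1 follows AEs to baseline or stability, but also allows follow-up to end at the final visit, which for a leaver may be the acute one. Section 12.3 requires SAE reporting from consent to 30 days after leaving. Two gaps remain: no contact is scheduled through which these duties would be met, and sections 10.1.9 and 12 start AE collection at first dose, which leaves Group 1 before Month 3 resting mainly on 12.3.

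**4. Scale.** Expected endpoint cases by Month 3 with 1000 per group: 0.20 × 1000 = 200 and 0.15 × 1000 = 150. Let f be the share of cases who leave because of the ARI, assumed equal in both arms. The documents give no value for f. Leavers = 200f v 150f; difference in the proportion without a later sample = (0.20 − 0.15) × f.

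| f (assumed) | Group 1 | Group 2 | Difference, percentage points |
|---|---|---|---|
| 5% | 10 | 7.5 | 0.25 |
| 10% | 20 | 15 | 0.5 |
| 25% | 50 | 37.5 | 1.25 |
| 50% | 100 | 75 | 2.5 |
| 100% (bound) | 200 | 150 | 5.0 |

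The synopsis limits the mechanistic endpoints to Brisbane. With 500 per group at 20% v 13.5%, the cases are 100 v 67.5, so f = 10% gives 10 v 6.75 and f = 50% gives 50 v 33.75.

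**The case against.** A reader might infer from 10.3 that everyone who reaches the primary endpoint leaves the study. The documents do not support that. Such an ARI is not a withdrawal condition in 9.3.1, the Unscheduled Visit is nowhere called an exit, and even people who stop the product are encouraged to stay. This stands, and it confines the point to those who actually leave because of the ARI.

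A reader might also infer that these leavers go without blood or any AE assessment. That is not so either. The Unscheduled Visit includes both, and its procedures are close to those of the closing visit, where blood is only encouraged. The exemption may simply have been meant to avoid a duplicate visit. Product return is covered in 9.3.1 and 11.4, and AE and SAE duties continue as set out above. What is absent is a specified later contact, and the explicit request for stop dates at exit.

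The serology loss is also partial. The secondary infection endpoint accepts PCR, and the swab at the acute visit is tested for COV, so a COV-caused ARI can be documented without later antibodies. Seroconversion as a component and as a mechanistic endpoint is not rescued in this way.

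Finally, 10.3 does not remove the primary event, which is already recorded when the worker leaves; the same holds for time to ARI. Section 13.2.1 restricts the intention-to-treat sample to people with at least one dose, which read literally could drop a Group 1 worker who leaves before Month 3. That is a separate defect of the analysis set and does not follow from the exemption.

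**Conclusion.** The point holds in limited form. Section 10.3 treats an endpoint ARI as a reason to discontinue, in conflict with 9.3.1, and leaves the workers who do discontinue for it with no specified contact after the acute visit. The data at risk are post-acute serology, symptom days and AE stop dates, so secondary, mechanistic and safety results are affected rather than the 3-month event count.

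The size is unknown because the leaving share is not in the documents. It runs from 10 v 7.5 people at 5% to a bound of 200 v 150. That bound, 350 of 2000 or 17.5%, should not be read as an expected loss. The counts assume the plan's rates, which apply a COV infection figure to ARI, events by Month 3 only, and the same leaving share in both arms. With a small leaving share the imbalance between arms is a fraction of a percentage point.

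Nor should all the follow-up time lost by leavers be charged to the missing visit. One closing visit recovers a sample and a review of symptoms, not months of daily reports. Those depend on keeping endpoint cases in the study, which is why the wording on participation matters as much as the visit. Severity: should be fixed.

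**What to change.** Three changes, all about data collection; they say nothing on whether study treatment continues.

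- **Section 10.3:** delete the clause that limits the visit to people leaving for reasons other than an endpoint ARI, so that every leaver is asked to attend.
- **Section 10.3, timing:** for these leavers, place the visit at the next scheduled visit date rather than alongside the Unscheduled Visit. Without this, deleting the clause could produce two acute visits and no later serology. For Group 2 the final visit date must first be reconciled, since section 10.2 gives 6 months and Appendix 1 gives Day 120.
- **Sections 9.3.1 and 10.2:** state that an endpoint ARI does not end study participation, and that daily SMS, scheduled visits and AE/SAE collection continue after the Unscheduled Visit. Correct the cross-reference in 9.3.1, which points to section 10.4 although the early withdrawal text is in 10.3.

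The cost is a short amendment and one visit of an existing type for each such leaver, which is likely to be few. Participants may still decline, so the change reduces the loss without removing it.
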